## **Study Protocol**

### **"IMPACT OF A PREOPERATIVE OUTPATIENT EDUCATION PROGRAM FOR OSTOMY PATIENTS: A COHORT-COMPARATIVE PILOT STUDY"**

#### **Introduction**

Data reported from Spanish Ostomy Association estimate that 1.5% of total population are living with an ostomy. Colorectal cancer is the most common diagnosis associated with stoma formation (80% of the total cases), followed by inflammatory bowel disease in about eight per cent. Currently there's no doubt about the role of specialized nurse in health education relative to stoma care and adaptation process. Preoperative stoma site marking is widely recommended by the main Scientific Societies related to colorectal and urological cancer. It is one of the most impactful measures provided by stoma care specialist nurses, as patients have less stoma-related complications and higher postoperative health-related quality of life scores.

Stoma creation after colorectal surgery is recognized in some studies as an independent cause of prolonged hospital stay and readmissions. However, other publications have not confirmed this point. Gumbo et al, in a retrospective study, reported no differences in postoperative complications or postoperative stay including readmissions between patients who underwent anterior rectal resection and anastomosis with or without a diverting ileostomy, in the setting of a multidisciplinary team and a multimodal rehabilitation program. Studies suggest that preoperative education and counseling has proven to result in significantly better competence in self-care stoma and enhancement in self-management of complications. Nevertheless, there is a lack of data regarding the optimal timing of planned teaching. Studies developed in other fields like breast cancer surgery, indicate that women

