postoperatively experience a decreased ability to direct attention and perform tasks. This is consistent with the study published by Cupples concerning recovery from cardiac surgery, concluding that patients who received education 5 to 14 days preoperatively, a preoperative phone call, as well as postoperative teaching, had higher preoperative knowledge and lower postoperative anxiety states than patients who only received preoperative teaching after admission to the hospital. Additionally, the incorporation of minimally invasive surgery results in shorter hospitalizations and less time gaining proficiency in stoma management.

Up to date, conventional practice in our team involved stoma education being imparted postoperatively. Given that, we questioned if implementing a preoperative program could influence postoperative course in new ostomate patients. The purpose of this study is to evaluate the effectiveness of preoperatively education in the outpatient setting in reducing length of stay for stoma patients, compared to standard postoperative care. Secondary end points will be minor and major morbidity, mortality, reoperation and readmission rates assessment.

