### Material and Methods

Consecutive colorectal surgery patients undergoing stoma formation in a single center will be recorded in a cohort study, during a 12-month period. Records will be retrospectively collected before outpatient information program establishment and prospectively in the second study period. Data and personal identities of individual participants are coded to ensure patient confidentiality. Patients in the standard group received stoma education after surgery, during hospital stay, and patients in the intervention group received the same information preoperatively in outpatient setting.

Inclusion criteria considered for scheduled preoperative clinic visit: patients older than 18 years of age undergoing elective colorectal resections that eventually would require formation of a stoma (colorectal cancer up to 20 cm from the anal verge, colonic poliposis and inflammatory bowel disease). Patients will be excluded from the study if they already had a stoma before the operation or in case of emergent surgery.

Patients in the study group have one individual consultation 45 minutes in duration several days before surgery with the stoma nurse specialist, following standard ostomy teaching plans (displayed in Table 1).

1. General information about what is a stoma and different types of stoma
2. Potential surgical procedure
3. Information about stoma marking (benefits and timing to perform)
4. How to care your ostomy
5. Effect of the diet on ostomy management
6. An overview on dietary advice
7. *Types of ostomy bags*
8. Complications that may arise after an incorrect apply of a new pouching system
9. How to manage peristomal skin irritation if necessary
10. Influence of stoma on quality of life
11. *Sports and fitness activities you are able to do with a stoma*
12. How and where get the pouches
13. Who to ask if you are in doubt about any procedure
14. Information for family and caregivers

Table 1. Information for ostomy patients

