In both groups and in all cases, the stoma site will be marked the same day of surgery. Patients, except for specific contraindication, follow the Enhanced Recovery Pathways established in our colorectal Unit and approved by Local Quality Committee. All procedures will be performed or supervised by a specialist *colorectal* surgeon. Patients, irrespective of the group, are visited in the ward by the enterostoma therapist one or two days after stoma creation, emphasizing basic skills to optimize the ability to perform independently stoma care.

The discharge and readmission criteria are similar for both treatment groups and followed conventional protocols and care pathways set in our working group.

Data collected included age, gender, American Society of Anesthesiologists (ASA) grade, diagnosis, surgical approach and type of stoma. Measurement variables are complications and mortality rates (assessed by Clavien-Dindo Classification), reinterventions, readmissions within the first 30 days after surgery and length of hospital stay. Similar data will be retrospectively collected for patients prior to the introduction of the preoperative education program.

All statistical analyses are performed using SPSS version 20 (SPSS Inc., Chicago, IL, EE. UU.).

Continuously variables were tested by Students T-test, Mann-Whitney U for numerical variables and Pearson's Two-sided Chi-square Test for dichotomous variables or Fisher test for qualitative variables. An alpha level of .05 was used to determine statistical significance.

The article will be reported in line with the STROCSS criteria.

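### Does leaving length of stay undefined, and recording readmission only as a rate, put the main comparison at risk?

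*Combined protocol and SAP*

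**What the plan says.** The Introduction sets out to judge how effective preoperative outpatient education is "in reducing length of stay for stoma patients, compared to standard postoperative care". Its list of secondary end points closes with "mortality, reoperation and readmission rates assessment".

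Material and Methods gives the measurement variables, ending with "readmissions within the first 30 days after surgery and length of hospital stay". No section states the first or last day of the stay, the handling of readmission days, or the handling of patients who die in hospital. Duration of readmission is not listed as an outcome.

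The control group comes from past records: "Similar data will be retrospectively collected for patients prior to the introduction of the preoperative education program". Stay and readmission are joined in only one place, the Introduction's account of a cited retrospective study, which compared "postoperative complications or postoperative stay including readmissions between patients" with and without a diverting ileostomy.

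**The concern.** Two things look wrong.

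- **The main outcome has no written definition.** One group is retrospective and the other prospective. If readmission days, or a night in hospital before surgery, were counted in one period and not in the other, the discrepancy would appear as an effect of the programme.
- **Readmission is planned as a proportion.** On the index-stay reading, the outputs show how many patients come back but not for how long. A shorter index stay could then overstate the net saving if readmissions rise. It could understate it if they fall, which is plausible given that the Introduction cites "better competence in self-care stoma and enhancement in self-management of complications" after preoperative education.

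The apparent remedy is to define the stay and to add total hospital days from surgery to day 30. At stake would be whether a reported reduction in stay is a real reduction in hospital use.

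**Working it through.** The plan states no sample size, standard deviation, expected stay or readmission rate, so there is no figure to reproduce. The inputs below are assumptions: 10 to 20% readmitted, 5 to 7 days per readmission, index discharge on day 7, 30 patients per group, standard deviation 5 to 7 days. Means are used to show scale; the plan itself would compare stay by t-test or Mann-Whitney test.

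**1. Which reading does the text support?** The Introduction names stay as the purpose and readmission as a secondary end point. Material and Methods again lists them as two variables. Where a stay that includes readmissions is meant, in the cited study, the text says so. Index stay is therefore the natural reading.

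**2. What would mixing the definitions cost?** Readmission days per enrolled patient = rate × duration: 0.10 × 5 = 0.5 day to 0.20 × 7 = 1.4 days. This error arises only if the two periods are coded differently, and the plan calls for similar data in both. A fixed number of preoperative days counted in both groups cancels in the difference.

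**3. How far could readmission move the net saving?** With discharge on day 7, 23 days remain to day 30, and late readmissions are cut off at day 30.

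- Readmission day uniform over 23 days: (18 × 5 + 5 × 2.5)/23 = 4.46 days; (16 × 7 + 7 × 3.5)/23 = 5.93 days.
- Readmission mostly early (hazard 0.012 per day for 10 days, then 0.003): the probability of readmission by day 30 is 1 − exp(−0.159) = 0.1470. The parts falling in the last 5 and last 7 days are 0.0129 and 0.0181. Days counted: 5 − 2.5 × 0.0129/0.1470 = 4.78; 7 − 3.5 × 0.0181/0.1470 = 6.57.

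Two rates that both lie between 10 and 20% differ by at most 10 points. The shift is 0.10 × 4.46 = 0.45 to 0.10 × 6.57 = 0.66 day, in either direction. At the upper figure, a 1-day index saving becomes 1 − 0.66 = 0.34 to 1 + 0.66 = 1.66 days. Cancelling it needs 1/6.57 = 15.2 to 1/4.46 = 22.4 extra points, which is outside the assumed range.

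**4. Could total days to day 30 resolve that shift?** Half-width of the 95% interval = 1.96 × SD × √(2/30): 2.53 days for SD 5 and 3.54 days for SD 7. To bring the half-width down to 0.66 day needs n = 2 × (1.96 × SD/0.66)² per group: about 441 for SD 5 and 864 for SD 7.

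**5. How much hangs on the death rule?** Take one death on day 3 in a group of 30 whose mean is 10.

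- Total days to day 30: scoring the death as 30 days moves the mean by (30 − 10)/30 = 0.67 day compared with excluding it. That is as large as the biggest shift in step 3.
- Index stay: counting the actual 3 days moves the mean by (3 − 10)/30 = −0.23 day.

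**6. Does the readmission window distort the rate?** It runs from surgery, so discharge on day 10 leaves 20 days at risk and discharge on day 7 leaves 23. With a constant hazard of 0.003 to 0.009 per day, 1 − exp(−ht) differs by 0.84 to 2.23 points. In a group of 30 that is 0.25 to 0.67 of a patient.

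**The case for a change.** The best case for a change is that the main outcome of any study deserves a start, an end and a rule for deaths. This matters more when one group is abstracted from old records, and writing it down costs a few lines. Rates can also hide days: with 20% readmitted in both groups but mean readmissions of 9 and 4 days, the rates are identical while hospital use differs by 0.20 × 9 − 0.20 × 4 = 1.0 day per patient. Only patients already counted as readmitted would need extra data, 3 to 6 per group at the assumed rates.

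What stands is that the definition is missing, that the start point (admission or surgery) is truly unstated, and that the published report should say which was used. What does not stand is the step from there to a faulty comparison. Nothing in the documents points to different coding by period. The 1.0-day example needs a 5-day gap in readmission length between groups, and at the assumed 5 and 7 days it is 0.20 × 2 = 0.4 day. Either figure lies well inside an interval of plus or minus 2.5 to 3.5 days. Readmission dates may also be less complete in the retrospective group, so the added outcome could carry a bias of its own.

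**Conclusion.** The concern does not call for a change. The missing definition is a gap that an analyst fills sensibly, with one start point, index discharge as the end, and the same rule in both periods. Following the plan on its natural reading gives no wrong result. Readmission and mortality are already reported beside the stay, so a rise in either would be seen.

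Total hospital days to day 30 would be a reasonable descriptive extra, but its absence is not a flaw in a single-centre pilot. It would leave the primary result as it is. It targets a shift of 0.45 to 0.66 day with an interval of plus or minus 2.5 to 3.5 days, and one death can move it by 0.67 day depending on the scoring rule.

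These sizes rest on the assumed 10 to 20% readmission, 5 to 7 days per readmission, discharge on day 7, 30 patients per group and standard deviations of 5 to 7 days. The judgement would change if the records showed that stay had been coded differently in the two periods. The documents give no sign of that.

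### Counting readmissions to day 30 after surgery gives shorter-stay patients more days at risk; a count over 30 days from discharge should be reported alongside it

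*Combined protocol and SAP*

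**What the plan says.** The last paragraph of the Introduction sets the purpose: to find out whether preoperative outpatient education is effective "in reducing length of stay for stoma patients, compared to standard postoperative care". The same paragraph continues: "Secondary end points will be minor and major morbidity, mortality, reoperation and readmission rates assessment". It gives none of these a time window.

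Material and Methods gives the only outcome window in the document, in a list that ends "readmissions within the first 30 days after surgery and length of hospital stay". The items before length of stay read: "Measurement variables are complications and mortality rates (assessed by Clavien-Dindo Classification), reinterventions, readmissions within the first 30 days after surgery". The clock starts at surgery. The sentence does not settle whether the 30 days belong to readmission alone or to every event in the list.

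The statistical paragraph of the same section compares categorical outcomes by chi-square or Fisher tests at the 5% level. It describes no person-time or time-to-event method.

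On data collection, the section says "Records will be retrospectively collected before outpatient information program establishment and prospectively in the second study period". It adds that "Similar data will be retrospectively collected for patients prior to the introduction of the preoperative education program" and that "The discharge and readmission criteria are similar for both treatment groups". It does not say how events after discharge are found in either cohort.

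**The concern.** A window counted from surgery includes the index admission, during which a readmission cannot occur. The time in which one can be counted is what remains after discharge, so it shrinks day for day as the stay lengthens. In most studies this is a minor matter. Here the quantity that sets the time at risk is the outcome the programme is meant to change.

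If the programme succeeds, its patients leave hospital earlier and have more days in which a return counts. A simple comparison of proportions would then tend to show more readmissions with the programme, even if the risk on each day after discharge were the same in both cohorts. Readers who see a shorter stay will naturally ask whether it was bought with more readmissions, and this is the comparison they would use to answer that. An excess produced by the counting rule could be taken for harm.

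**Working it through.** **Inputs from the document.** The window is 30 days from surgery (Material and Methods). The intended effect is a shorter stay (Introduction). The analysis is a crude comparison of proportions (Material and Methods). The document gives no sample size, expected stay or readmission rate, so there is no figure of its own to reproduce.

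**Assumed inputs.** Observed readmission in the standard group is 15%. Mean stay falls from 10 to 7 days, or from 14 to 8 days, and each group is treated as if every patient had the mean stay. The programme has no effect on the risk of readmission at a given time after discharge.

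**Step 1: days at risk = 30 − stay.**
- 10 to 7 days: 20 against 23 days at risk, ratio 23/20 = 1.15.
- 14 to 8 days: 16 against 22 days at risk, ratio 22/16 = 1.375.
- Equal stays: ratio 1, no artefact.
- A stay of 30 days or more: no days at risk.

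**Step 2: constant daily hazard after discharge.** The 15% rate corresponds to a cumulative hazard of −ln(0.85) = 0.1625. With standard-group stay L0 and programme-group stay L1, the daily hazard is h = 0.1625/(30 − L0) and the programme-group rate is 1 − exp(−h(30 − L1)).
- 10 to 7 days: h = 0.1625/20 = 0.00813; 1 − exp(−0.00813 × 23) = 17.0%, an excess of 2.0 points.
- 14 to 8 days: h = 0.1625/16 = 0.01016; 1 − exp(−0.01016 × 22) = 20.0%, an excess of 5.0 points.

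**Step 3: front-loaded hazard.** If readmissions cluster soon after discharge, the extra days at the end of the window matter less. Take cumulative hazard A(1 − exp(−t/10)) at t days after discharge, that is, exponential decay with a mean of 10 days, and set A so that the standard group again shows 15%.
- 10 to 7 days: A = 0.1625/(1 − exp(−2.0)) = 0.1625/0.8647 = 0.1880. At 23 days the cumulative hazard is 0.1880 × 0.8997 = 0.1691, and the rate is 15.6%, an excess of about 0.6 points.
- 14 to 8 days: A = 0.1625/(1 − exp(−1.6)) = 0.1625/0.7981 = 0.2036. At 22 days the cumulative hazard is 0.2036 × 0.8892 = 0.1811, and the rate is 16.6%, an excess of about 1.6 points.

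| Stay, standard to programme | Days at risk | Excess, front-loaded | Excess, constant |
|---|---|---|---|
| 10 to 7 days | 20 to 23 | 0.6 points | 2.0 points |
| 14 to 8 days | 16 to 22 | 1.6 points | 5.0 points |

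**Step 4: the discharge-based count.** With 30 days from discharge, every patient discharged alive has the same 30-day window whatever the stay. The difference in days at risk is zero, and under either hazard above so is the artefact.

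**The case against.** The strongest reply is that a window starting at surgery is a legitimate choice. It gives every patient the same postoperative period. A patient sent home early who comes back on day 8 is a real readmission and a real cost of early discharge, so whether to call the excess an artefact depends on the question asked. A discharge-based window also has an imbalance of its own: with stays of 7 and 10 days it compares postoperative days 7 to 37 with days 10 to 40, and these differ if risk falls with time since surgery. This stands. It is why the count from surgery should be kept, and why the discharge-based figure is proposed as an addition.

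It is also fair that the effect is small for modest changes in stay, works against the programme, and leaves the measurement of length of stay untouched, in what the title calls a pilot study. A bias against the programme can still suggest harm where there is none, so the point survives at moderate weight.

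Two stronger readings are tempting, and the document supports neither. A reader might infer that event capture does differ between the cohorts. Through this mechanism that needs a difference in stay, which is the hypothesis and not a documented fact. A reader might also infer that complications, deaths and reinterventions are biased, either because they are counted to discharge or because the earlier cohort's records are searched for longer. Nothing in the text says either. The 30-day phrase can be read as covering the whole list, and on that reading those events already have a fixed window whose length does not depend on stay.

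**Conclusion.** The point holds for readmission, conditionally. As written, the rule ties time at risk to the primary outcome, and the planned tests do not correct for it. If the programme shortens stay, the readmission comparison will tend to look worse for the programme than the risk per day after discharge warrants. Over the scenarios examined the excess ranges from about 0.6 to 5.0 points. The top of that range needs both a large cut in stay (6 of 14 days) and a constant daily hazard. All these sizes rest on assumed stays, an assumed 15% rate and assumed hazard shapes.

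For complications, deaths and reinterventions, what remains is an ambiguity to clear up, not a demonstrated bias. Collecting one cohort retrospectively and the other prospectively makes an explicit common rule more useful, but does not by itself show unequal capture. This is a change the plan should make; it does not put the primary comparison in doubt.

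**What to change.** Keep the count of readmissions within 30 days of surgery. Add readmission within 30 days of discharge, for patients discharged alive, in both cohorts. State in advance that the discharge-based figure will be used when judging whether a shorter stay came with more readmissions.

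As a clarification only, state that the 30-day window from surgery also applies to complications, deaths and reinterventions, that events after discharge are included, and that they are sought in the same way in the retrospective and prospective cohorts.

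The cost is two or three sentences in Material and Methods and a chart look-up extended to 30 days after discharge: for a 10-day stay, to day 40 after surgery instead of day 30. No extra patients or visits are needed.

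### Length of stay is compared between a pre-programme and a later cohort by unadjusted tests only, so a difference in case mix could create or hide an education effect

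*Combined protocol and SAP*

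**What the plan says.** The purpose stated in the Introduction is to "evaluate the effectiveness of preoperatively education in the outpatient setting in reducing length of stay for stoma patients", against standard postoperative teaching. Material and Methods defines the two groups by period: "Records will be retrospectively collected before outpatient information program establishment and prospectively in the second study period". For the earlier group, "Similar data will be retrospectively collected for patients prior to the introduction of the preoperative education program". No randomisation, matching, stratification or weighting is described.

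The recorded variables are listed in Material and Methods: "Data collected included age, gender, American Society of Anesthesiologists (ASA) grade, diagnosis, surgical approach and type of stoma".

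The statistical paragraph of the same section reads "Continuously variables were tested by Students T-test, Mann-Whitney U for numerical variables", adds chi-square and Fisher tests for categorical variables, and sets alpha at .05. It does not say which of the first two tests applies to length of stay. Both are unadjusted, so the point is the same either way. No regression or other adjusted analysis appears anywhere in the document.

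The Introduction also says that "the incorporation of minimally invasive surgery results in shorter hospitalizations". By the protocol's own account, then, at least one recorded variable (surgical approach) is related to the main outcome.

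**The concern.** Group and calendar period are the same thing here, so any prognostic difference between the patients of the two periods enters directly into the crude difference in stay. If the later cohort has more minimally invasive operations, or fitter patients, stay falls without any help from the programme. If it has fewer, or sicker patients, a real benefit is partly or wholly cancelled.

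The listed tests could be used on baseline variables and might reveal an imbalance, but revealing it does not correct the length-of-stay comparison. In small groups a non-significant baseline test is also weak evidence of balance.

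What is at stake is the main conclusion. It is framed as effectiveness and judged at alpha .05, yet the stated analysis cannot separate the programme from measured case mix, although the plan already calls for the variables that would allow it.

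**Working it through.** **Inputs from the protocol.** Alpha is .05. There is no sample size, SD, approach effect, expected benefit or case-mix figure, so there is no stated calculation to reproduce. Everything below is illustration under assumed inputs: SD 5 days; stay 2 or 4 days shorter with minimally invasive surgery; its share 10, 20 or 30 points higher or lower in the later cohort; 15 to 60 patients per group.

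**Step 1: bias.** Bias in days = approach effect × difference in share. The range runs from 2 × 0.10 = 0.2 days to 4 × 0.30 = 1.2 days. It does not depend on sample size.

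**Step 2: creating an effect.** With no true effect, the two-sided t-test has 2n − 2 degrees of freedom and non-centrality bias / (5 × √(2/n)). For example, with bias 0.8 days and n = 30, this is 0.8 / (5 × √(2/30)) = 0.62, and the rejection probability is 0.094.

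| Bias (days) | n=15 | n=20 | n=30 | n=40 | n=60 |
|---|---|---|---|---|---|
| 0.2 | 0.051 | 0.052 | 0.053 | 0.054 | 0.055 |
| 0.4 | 0.055 | 0.057 | 0.061 | 0.064 | 0.072 |
| 0.6 | 0.062 | 0.066 | 0.074 | 0.083 | 0.100 |
| 0.8 | 0.071 | 0.078 | 0.094 | 0.109 | 0.140 |
| 1.2 | 0.097 | 0.115 | 0.150 | 0.185 | 0.256 |

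Sensitivity to the SD, at 0.8 days: with SD 4 the range from 15 to 60 per group is 0.083 to 0.192; with SD 7 it is 0.061 to 0.095.

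**Step 3: hiding an effect.** Assume a true 2-day benefit and a shift against the programme, so that the apparent benefit is 2 minus the bias. The entries are the probability of a significant result in the benefit direction.

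| Apparent benefit (days) | n=15 | n=20 | n=30 | n=40 | n=60 |
|---|---|---|---|---|---|
| 2.0 (no shift) | 0.184 | 0.234 | 0.331 | 0.423 | 0.584 |
| 1.8 | 0.157 | 0.198 | 0.278 | 0.356 | 0.498 |
| 1.2 | 0.093 | 0.111 | 0.148 | 0.184 | 0.256 |
| 0.8 | 0.062 | 0.071 | 0.088 | 0.105 | 0.138 |

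**Step 4: skewed data, and adjustment.** Length of stay was simulated as log-normal (6,000 datasets per setting), with assumed means of 12 days open and 8 days minimally invasive and a coefficient of variation of 0.45. Results are for 15/20/30/40/60 per group.

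- *Share rising from 50% to 70%, no true effect.* The expected crude ratio of geometric means is exp(0.20 × ln(8/12)) = exp(−0.081) = 0.92. The t-test rejects in 0.066/0.084/0.099/0.112/0.146 and Mann-Whitney in 0.065/0.084/0.097/0.116/0.158. Log-scale regression adjusted for approach rejects in 0.052/0.049/0.047/0.050/0.046, with a ratio of 1.00.
- *Share falling from 50% to 30%, true ratio 0.80.* The expected crude ratio is 0.80 × exp(0.081) = 0.87. The t-test detects the benefit in 0.116/0.147/0.199/0.257/0.357 and the adjusted model in 0.259/0.342/0.477/0.610/0.786, with a ratio of 0.80.

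A second simulation used different assumptions: a factor worth one residual SD on log stay, differing by 20 to 30 points between cohorts, and no true effect. The t-test rejected in 9–16% of runs at 30 per group and 22–41% at 100. The adjusted model stayed near 5%. Crude ratios were about 0.86 to 0.91.

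**Step 5: price of adjustment.** The table gives the ratio of adjusted to crude confidence-interval half-width over six assumed settings (3,000 datasets each).

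| n per group | 3 covariate terms | 9 covariate terms |
|---|---|---|
| 15 | 0.98–1.12 | 1.15–1.29 |
| 20 | 0.97–1.09 | 1.07–1.20 |
| 30 | 0.95–1.07 | 1.01–1.14 |

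**The case against.** The best defence is that the design already limits the problem. It is a single-centre study with consecutive recording ("Consecutive colorectal surgery patients undergoing stoma formation in a single center will be recorded in a cohort study, during a 12-month period"), a common recovery pathway, surgery performed or supervised by a specialist, the same ward visit for both groups and similar discharge criteria. If the 12 months cover both cohorts, there is little time for case mix to drift. These features do limit differences in care and selection. They do not balance the patients or the procedures, and eligibility mixes cancer, polyposis and inflammatory bowel disease.

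The figures rest entirely on assumed inputs, and this objection stands. The 26% needs the largest effect, the largest shift and the largest group size together. With a 2-day effect and a 10- to 30-point rise, the false-positive rate is only 5.1% to 7.4% at 15 to 30 per group, and the title calls this a pilot. Nothing in the documents shows that a shift occurred, and the remark on minimally invasive surgery is general background. If anything it hints at a rise, so the masking case has less support in the text. The bias in the estimate, however, does not shrink with group size.

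That adjustment works in the simulations is partly by construction, because approach is the only confounder and is measured without error. In practice it removes only the recorded part. The completeness of older records is not promised.

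The eligibility heading ("Inclusion criteria considered for scheduled preoperative clinic visit") ties the criteria to a visit that belongs to the programme. The exclusions in the same paragraph are worded for the whole study. This is an ambiguity about selection that adjustment would not settle, and the concern does not depend on it.

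**Conclusion.** The concern holds and should be fixed. The planned length-of-stay comparison is crude, the groups are non-randomised before-after cohorts, and the protocol itself identifies a recorded variable related to stay. Any difference in case mix between periods would therefore be read as programme effect, or would offset one.

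That conclusion does not depend on the numbers. The size does, and it cannot be known from the documents. Over the assumed range, false positives run from about 5% (no material inflation) to 26%. The chance of detecting a 2-day benefit falls from 18% to 6%–16% at 15 per group, from 33% to 9%–28% at 30, and from 58% to 14%–50% at 60.

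**What to change.** Make the primary analysis a prespecified regression of length of stay on group. The log scale is one suitable choice, giving an adjusted ratio of geometric means with a 95% confidence interval.

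- Adjust for a short set of the recorded baseline and surgical variables that includes surgical approach. Fix their order of entry in advance (for example approach, ASA grade, stoma type, diagnosis), so that the number of terms depends only on the final sample size.
- Do not adjust for complications or reinterventions, which are outcomes.
- State how patients with missing covariates in the retrospective records will be handled.
- Tabulate case mix by period, and keep the unadjusted test as a supporting analysis.
- Word the conclusion as an adjusted before-after association. Calendar time, mode of data collection and unmeasured differences remain confounded with the programme.

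The cost is analysis-plan wording and a few lines of SPSS, with no new patients and no variables beyond those listed. The interval may widen, in the assumed settings by up to about 12% with 3 terms and 29% with 9 terms at 15 per group, and by up to 7% and 14% at 30. That is the reason to keep the covariate set short. The adjusted effect may turn out smaller or larger than the crude one.

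### Does it matter that the plan never says which test length of stay receives, and plans no effect estimate or confidence interval?

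*Combined protocol and SAP*

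**What the plan says.** The Introduction gives the purpose as judging whether preoperative outpatient education is effective "in reducing length of stay for stoma patients, compared to standard postoperative care". It continues: "Secondary end points will be minor and major morbidity, mortality, reoperation and readmission rates assessment". The word primary is not used, but length of stay is the only outcome left in that role.

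In Material and Methods the list of measurement variables ends with "readmissions within the first 30 days after surgery and length of hospital stay". The statistical paragraph then has three parts:

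- for quantitative variables, "Continuously variables were tested by Students T-test, Mann-Whitney U for numerical variables";
- for categorical variables, "Pearson's Two-sided Chi-square Test for dichotomous variables or Fisher test for qualitative variables";
- the decision rule, "An alpha level of .05 was used to determine statistical significance".

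It does not mention length of stay, a normality check, an effect estimate or an interval. Only the chi-square test is called two-sided. The same section commits the article to the STROCSS reporting criteria. The title describes the work as "A COHORT-COMPARATIVE PILOT STUDY", and no sample size or power is stated.

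**The concern.** Length of stay is both continuous and numerical, so the sentence assigns it to two tests at once. On skewed data the t-test and Mann-Whitney U can fall on opposite sides of .05. The control records are collected retrospectively, so an analyst could in principle look at the data before choosing. If both tests were run and the better one reported, the false-positive rate would exceed the stated level.

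The missing estimate adds to this. In a pilot with no sample-size basis, a p-value alone does not say how many days were saved or how precisely that is known. At stake would be the credibility and usefulness of the result on the main outcome.

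**Working it through.** **Nothing to reproduce.** The plan gives no sample size, standard deviation, expected effect or power. The only figure it supplies is alpha = .05. Every other input below is an assumption.

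**Assumptions.** Stays are log-normal, rounded to whole days (minimum 1), with a control median of 8 days. The log-scale SD is 0.5, 0.7 or 0.9, with 0.3 and 0.4 as milder skew. Groups are 30 v 30, 40 v 40 or 30 v 60, with 60 v 60 as a sensitivity case. The effect is either none or a stay 25% shorter (ratio 0.75). Tests are two-sided: equal-variance t and asymptotic Mann-Whitney U. The main runs used 8,000 trials per setting.

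**Step 1: always t against always Mann-Whitney, ratio 0.75.** Share of trials in which the verdicts at .05 differ:

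| Groups | log-SD 0.5 | 0.7 | 0.9 |
|---|---|---|---|
| 30 v 30 | 13.2% | 14.0% | 12.5% |
| 40 v 40 | 12.0% | 16.2% | 15.8% |
| 30 v 60 | 13.4% | 17.2% | 17.1% |
| 60 v 60 | 8.8% | 18.0% | 19.6% |

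At log-SD 0.3 to 0.4 the share is about 1% to 10% for the three smaller designs. A separate set of runs (ratio 0.8, 20 to 100 per group, log-SD 0.4 to 0.8) gave 2% to 21%. A fair overall statement is about 1% to 20%.

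**Step 2: cost of settling on either test.** Under no effect, each test alone rejected in about 4.0% to 5.5% of trials in that separate set, so both are valid. Under ratio 0.75, Mann-Whitney has 1.1 to 5.9 points more power than t in the three smaller designs. At 40 v 40 and log-SD 0.7, for example, the figures are 42.1% and 37.1%, a gap of 42.1 − 37.1 = 5.0 points. At 60 v 60 the gap is 2.6 to 9.1 points.

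**Step 3: the conventional split.** Use Mann-Whitney if Shapiro-Wilk gives p < .05 in either group, otherwise t.

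- In the three smaller designs under no effect, at log-SD 0.5 to 0.9, the split picks Mann-Whitney in 94% to 100% of trials.
- Type I error in those settings is 4.5% to 5.3%.
- Under ratio 0.75 its verdict differs from a Mann-Whitney test fixed in advance in 0% to 0.4% of trials at log-SD 0.5 to 0.9, for all four designs (3,000 trials per setting). With log-SD 0.3 and 0.4 included, the maximum is 0.7%. A repeat with 2,500 trials per setting stayed within that limit.

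**Step 4: the worst behaviour.** If both tests are run and the smaller p-value kept, type I error at log-SD 0.5 to 0.9 is 6.5% to 7.0% in the three smaller designs and 6.8% to 7.4% at 60 v 60. Nothing in the plan provides for this.

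**Step 5: the estimate.** With ratio 0.75 the same effect can be stated in three ways:

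- as a ratio, 0.75;
- as a difference in medians, 8 − 0.75 × 8 = 2 days;
- as a difference in means, 0.25 × 8 × exp(SD²/2), which before rounding to whole days is 2.27, 2.56 and 3.00 days at log-SD 0.5, 0.7 and 0.9.

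A Hodges-Lehmann shift would carry a 95% interval of about ±1.6 to ±3.1 days in the three smaller designs. That is useful information, but any of these summaries could reasonably lead, and each can be computed from data the study already collects.

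**The case for a change.** The strongest case for a change is that the normality split is nowhere written. Without it the analyst is free to choose, and the verdict could differ in up to about one trial in five if the t-test were used whatever the skew. Naming one test would take a sentence, would cost no patients or data, and would also settle sidedness, which is stated only in "Pearson's Two-sided Chi-square Test". A pilot with no power calculation is better read through an interval than a p-value, and the STROCSS commitment does not itself name an estimate or interval in this document.

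Some of this stands. The sentence is ambiguous, and a named test with an interval would be better drafting. The content of STROCSS is not in the documents, so it neither supplies the interval nor shows that one will be missing. What does not stand is the inference that the main result is at risk. The large disagreement figures compare two fixed policies, one of which ignores skew. Under ordinary practice the choice is nearly always Mann-Whitney, which the plan already lists. Two-sided testing at .05 is the normal default for both tests.

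**Conclusion.** No change to the plan is called for. This is missing detail that an analyst fills sensibly. Under the conventional reading the verdict on length of stay matches a pre-named Mann-Whitney test in over 99% of simulated trials, and type I error stays near 5%. Even if one test were applied throughout, either would be valid; the t-test would give up roughly 1 to 6 points of power in the designs with 30 to 60 per group, and up to about 9 points at 60 v 60. The ambiguity matters only if the t-test is used regardless of skew or the test is picked after seeing both results, and the plan proposes neither.

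The missing interval is a reporting matter. Adding one corrects no wrong rule or figure, and statisticians differ on whether a shift, a ratio or a mean difference should lead.

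These sizes rest on assumed log-normal stays with a median of 8 days, mainly 30 to 60 patients per group and a 25% reduction, none of which comes from the documents. The textual gap is certain; its numerical effect is illustrative. The comparison with historical controls is a separate question that the choice of test does not touch.
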